3.1. Hypothesis

The hypothesis that this study will try to demonstrate is that an educational intervention, based on the use of a web-app, will be effective in improving knowledge and risk behaviors for breast cancer in women between the ages of 25 and 45, residents in health area 7 of the Principality of Asturias.

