3.2. Objectives

3.2.1. Main Objetive

To evaluate the effectiveness of an educational intervention for the prevention of breast cancer risk through the use of a Web-App in women residing in health area VII of the Principality of Asturias.

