3.2.2. Specific Objetive

- Evaluate adherence to behavioral recommendations before and after after the educational intervention for each group separately.
- To compare adherence to behavioral recommendations after the intervention between the intervention and control groups.
- Evaluate, in each group separately, the knowledge in relation to the risk factors and symptoms of breast cancer before and after the intervention.
- To compare the level of knowledge in relation to the risk factors and symptoms of breast cancer between the intervention and control groups before and after the intervention.
- Estimate the risk and self-perception of developing breast cancer before and after the intervention for each of the groups.
- To compare the risk and self-perception of developing breast cancer between the intervention and control groups after the educational intervention.

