4.3. Data collection: tools and procedure

The data collection will take place during the months of March (pre-test) and June 2022 (post-test). At both times it will be done virtually, using a digital form. Participants will access this form through the project's web-app. The pre-test collection will be carried out after signing the consent and the post-test, after the educational intervention, that is, at 12 weeks.

At both moments, information will be collected related to personal, anthropometric, and behavioral variables (diet and physical activity), self-examination, knowledge related to risk factors and symptoms of breast cancer, perception of risk of developing breast cancer, and barriers to carry out. take actions to prevent it.

Additionally, after the educational intervention, satisfaction with the use of the web-app will be evaluated.

The information on the behavioral variables will be recorded using the Motiva.Diaf questionnaire. It includes 12 items that measure adherence to and motivation to carry out recommendations related to nutrition (questions 1 to 7) and physical activity (questions 8 to 12). Each item presents a Likert-type response format with a range from 0 (lack of motivation to make the recommendation) to 5 (intrinsic motivation). In addition, each separate recommendation can be interpreted dichotomously (makes=1 or does not make the recommendation=0). Finally, the synthetic variable adherence to healthy recommendations is elaborated as a result of scoring each item in its dichotomous interpretation (range 0=worst adherence to healthy recommendations to 12=greatest adherence to healthy recommendations).

The self-examination is carried out by means of the question, do you perform the breast self-examination once a month.

The information related to knowledge, risk perception and barriers with the MARA questionnaire. This questionnaire, specifically related to breast cancer, consists of 31 items that measure the following constructs: knowledge related to risk factors (9 items), knowledge related to signs and symptoms (9 items), perception of risk of developing breast cancer breast (6 items) and perceived barriers to carry out prevention strategies (7 items). Items related to knowledge have a score of 0 (error) and 1 (correct), therefore the range of scores, both for risk factors and for signs and symptoms, is between 0 and 9. The score of the other two scales is represented on a Likert-type scale ranging from 1

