(totally disagree) to 5 (totally agree), the total perception score being between 6 and 30 points (the lower the score, the lower the perception of risk and the barriers between 7 and 35 points (the lower the score, the fewer perceived barriers).

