5. STATISTICAL ANALYSIS

Initially, the normality of the distribution of the variables will be verified, the Kolmogorov-Smirnov test will be used. A description of the variables will be made using percentages, means (standard deviation) or median (interquartile range) depending on their nature and distribution.

To determine the association between variables, the chi-square test, McNemar for qualitative variables, will be used. For qualitative variables, they will be determined based on the distribution of variables.

Linear regression analyzes will be carried out to determine which variables best predict the score after the intervention in terms of knowledge about risk factors, signs-symptoms of early detection of breast cancer, knowledge and adherence to healthy behaviors.

The analyzes will be carried out using the IBM SPSS version 24.0®, considering that the results were statistically significant when the value of p is ≤ 0.05 .

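### No outcome or between-group comparison is designated to decide effectiveness, and every result is judged at p ≤ 0.05 without ranking

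*Combined protocol and SAP*

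**What the plan says.** - **Main objective (Section 3.2.1):** "To evaluate the effectiveness of an educational intervention for the prevention of breast cancer risk through the use of a Web-App". No outcome, time point or contrast is attached.
- **Hypothesis (Section 3.1):** the intervention "will be effective in improving knowledge and risk behaviors for breast cancer". This names two domains. It gives no explicit rule on whether both must improve or one is enough.
- **Specific objectives (Section 3.2.2):** six, unranked. Three look at each arm before and after, for example "Evaluate, in each group separately, the knowledge in relation to the risk factors and symptoms of breast cancer before and after the intervention". Three compare IG with CG: adherence, knowledge, and risk and self-perception.
- **Scores (Section 4.3):** adherence is a 0–12 score. Knowledge is two scales, and "the range of scores, both for risk factors and for signs and symptoms, is between 0 and 9". Risk perception is a 6-item score from 6 to 30.
- **Analysis (Section 5):** chi-square and McNemar tests, other tests chosen according to distribution, and regressions: "Linear regression analyzes will be carried out to determine which variables best predict the score after the intervention". All results share one threshold, "considering that the results were statistically significant when the value of p is" ≤ 0.05. No hierarchy is given, and nothing is labelled primary, secondary or exploratory.
- **Sample size (Section 4.2):** 361 women, to estimate one unnamed percentage of about 75% to within 5 points.
- **Registration (Section 6):** an entry in ClinicalTrials.gov is planned before the start.

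**The concern.** The trial randomizes women 1:1 against a no-intervention control. That protects the conclusion only if the conclusion rests on the IG-versus-CG contrast. As Sections 3 and 5 stand, a post-test difference in adherence or in either knowledge scale, or a before-after change within the IG, could each be presented as the evidence of effectiveness, and the choice could be made after the results are seen.

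Two things are at stake. First, the error rate of the overall claim is undefined, because it depends on an all-or-any rule that is not written down. Second, the within-arm tests make no use of the control group. Both arms answer the same questionnaires in March and June 2022, so repetition of the questionnaire or the change of season could shift both arms and make a before-after test significant with no effect of the intervention. Nor does a significant change in the IG beside a non-significant one in the CG test the difference between the groups.

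**Working it through.** **1. Which comparisons are in play.** Match the objectives in Section 3.2.2 to the scores in Section 4.3:

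- Post-test IG versus CG: adherence (1), knowledge (2) and perception (1), so four scores. Three of these belong to the hypothesis.
- A fifth outcome, risk, is named in the objectives, but Section 4 describes no way to measure it. The risk model appears only in the Introduction.
- Within-arm before-after: 4 scores × 2 arms = 8, or 6 if the risk and self-perception objective is only descriptive.
- Baseline IG versus CG: 2, because the knowledge objective asks for it.
- Total on the four scores: 8 + 2 + 4 = 14, or 6 + 2 + 4 = 12.

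**2. False-positive chance of the effectiveness claim, between-group tests only.** The inputs are 0.05 per test (Section 5), taken as two-sided because sidedness is not stated, and a pairwise correlation between outcomes of 0 to 0.5, which is assumed because the documents give none. For k independent tests the chance is 1 − 0.95^k. The values at correlation 0.5 come from the bivariate normal (k = 2) and from simulation of equicorrelated normals (k = 3 and 4).

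| Rule for claiming effectiveness | Correlation 0 | Correlation 0.5 |
|---|---|---|
| All hypothesis outcomes required | at most 5% | at most 5% |
| Either of two domains (one test each) | 1 − 0.95² = 9.75% | 9.1% |
| Any of three hypothesis scores | 1 − 0.95³ = 14.3% | 12.5% |
| Any of four scores, adding perception | 1 − 0.95⁴ = 18.5% | 15.6% |

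Counting only results that favour the intervention, any of three scores gives 1 − 0.975³ = 7.3% at correlation 0 and 6.3% at 0.5. No directional figure is given for the row with perception. Section 4.3 says "the lower the score, the lower the perception of risk", but not whether a lower or a higher perception is the favourable result.

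**3. What Section 5 offers as a group test.** The regressions look for predictors of the post-test score. Neither group nor the baseline score is named as a term, so they do not specify an estimate of the intervention effect.

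**4. Whether the sample size identifies the deciding comparison.** Reproducing the plan's figure: 1.96² × 0.75 × 0.25 / 0.05² = 288.1, and 288.1 / (1 − 0.20) = 360.1, rounded up to 361. It is correct for its own purpose, the precision of one percentage. It states no between-group difference, so it does not point to a primary outcome.

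The detectable difference for one comparison at 80% power and two-sided 0.05 is (1.960 + 0.842) × √(2/n per arm):

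- all 361 analysed (180.5 per arm): 0.295 SD;
- about 288 analysed after the 20% allowance (144 per arm): 0.330 SD;
- 144 per arm with baseline adjustment, multiplying by √(1 − r²): 0.315 (r = 0.3), 0.286 (r = 0.5) and 0.236 (r = 0.7), where r is an assumed pre-post correlation.

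**The case against.** The strongest reply is that the hypothesis joins knowledge and behaviour with an *and*. Read literally, both must improve, and requiring every outcome to be significant keeps the error at or below 5%. That reading is fair, and it is why no single inflated rate is put forward here. What stands against it is that neither Section 3 nor Section 5 turns it into a decision rule.

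Several stronger readings are tempting, and the documents do not support them:

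- *That no between-group comparison is planned.* Section 3.2.2 names one for every domain. What is missing is the designation of the one that decides.
- *That the plan takes a within-arm change as proof of effectiveness.* No section says so, and each within-arm objective has a between-group counterpart. No section excludes it either, so the point is one of principle.
- *That five contrasts inflate the error further.* The fifth is the risk outcome, which has no described measurement.
- *That the form of the adherence outcome is wholly open.* Section 4.3 allows each of the 12 items to be read as yes or no, but it then builds a named 0–12 score, and Section 5 models a score. The score is the natural reading.
- *That an unadjusted post-test comparison would be invalid.* Under 1:1 randomization it is valid. Baseline adjustment gains precision.

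The registry entry may name a primary outcome. It cannot be seen here, and it would still need to be carried into Section 5.

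**Conclusion.** The point holds as a gap in prespecification. Between-group comparisons exist, but none is tied to the main objective, within-arm objectives have equal rank, and one threshold covers all results.

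The false-positive chance of the effectiveness claim runs from at most 5% (all required), through about 9–10% (either domain), to 12.5–14.3% two-sided (any of three scores). With perception added it is 16–19%. These figures assume two-sided tests and a correlation of 0.5 to 0, and each holds only under its stated rule. A reader might infer that the trial's error rate is 14% or more; the documents do not support that, because they do not say that any one score suffices. The data remain usable and the remedy is wording, so this should be corrected but does not undermine the design.

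**What to change.** In Sections 3.2 and 5, before post-test data are analysed by group:

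- Designate the deciding IG-versus-CG comparison at 12 weeks. One option is a single primary outcome, for example the 0–12 adherence score. The other, which matches the hypothesis, is co-primary knowledge and adherence scores with both required at 0.05, stating which knowledge scale or scales count. The choice is the sponsor's. If a single knowledge score is chosen, the conclusion should be limited to that knowledge domain.
- Analyse it with a linear model of the post-test score on group and the baseline score already collected, two-sided 0.05, with a confidence interval.
- State that effectiveness is concluded only from that result.
- Label the other between-group outcomes secondary. Label within-arm changes, baseline comparisons and the predictor regressions descriptive or exploratory.
- State the detectable difference for a single comparison at 80% power: about 0.295 SD (all 361 analysed) to 0.33 SD (144 per arm) unadjusted, or 0.24–0.31 SD at 144 per arm after baseline adjustment, for an assumed correlation of 0.7 to 0.3.

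The cost is text only, with no new data or visits. The downside is less freedom to claim success on other outcomes, and lower power if both co-primaries are required. For example, two independent tests with 80% power each give 0.8 × 0.8 = 64% for both, and more if the outcomes are positively correlated.

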6. ETHICAL CONSIDERATIONS

In general, the precepts of the Declaration of Helsinki will be respected. This defines the principles that must be scrupulously respected by all the people involved in the present investigation. Specifically, informed consent will be requested, the free will to abandon the research will be respected without this causing any harm to the person, and the confidentiality of the data of the subjects participating in the study will be respected. The treatment, communication and transfer of personal data of all participants will comply with the provisions of Organic Law 3/2018, of December 5. The project has been

reviewed and authorized by the Research Ethics Committee of the Principality of Asturias and prior to its start it will be registered in ClinicalTrials.gov.

